6.0 Statistical Design

We will accrue a minimum of 10 patients and a maximum of 80 patients at a rate of 2 patients per month. The primary outcome for this trial is the time to progression or death. Patients treated with standard of care (observation) have median progression-free survival (PFS) of 24 months [10]. We will follow all patients for at least 24 months following treatment.

Patients will be randomized between observation and letrozole using a Bayesian adaptive algorithm [22]. Details of this methodology are given in the "Technical Details" section below. The first 10 patients will be randomized fairly between the 2 treatment arms. After 10 patients are enrolled there will be 5 patients on each treatment arm. As the trial progresses and data accrue the randomization will become unbalanced in favor of the treatment that, on average, has better results in terms of PFS, so that each successive patient is more likely to receive the treatment showing better results.

The trial will be stopped early and a treatment selected as being "better" if the probability is 0.90 or more that one treatment's PFS is longer than the other treatment's PFS. However, if all 80 patients are enrolled, then a treatment will be selected as being "better" if the probability is 0.80 or more that one treatment's PFS is longer than the other treatment's PFS.

The operating characteristics of this study design are summarized in Table 1. These operating characteristics are based on 1000 simulations of the study design for 6 possible scenarios.

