6.1 Outcomes

6.1.1 Primary Outcome

We will report the posterior probability that the letrozole arm has longer PFS than the observation arm. We will also provide a 95% posterior credible interval for the probability that the letrozole arm has longer PFS than the observation arm.

We will estimate the PFS with the Kaplan-Meier 23 product-limit estimator for each arm, and we will compare the PFS between the 2 arms with the log-rank test. We will model PFS with the Cox [24] proportional hazards regression model to estimate the hazard ratio for treatment (letrozole : observation), and we will construct the 95% confidence interval for this hazard ratio.

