6.2 Technical Details

Let MO and ML be the median PFS for treatments "observation" (O) and "letrozole" (L), respectively. We assume that MO and ML each have an inverse gamma prior distribution with mean 24 months and variance 57.6 months. The middle 95% of this prior distribution is between 13.4 and 42.6 months.

For each patient, the randomization probability for treatment O will be the posterior probability that it has the longer PFS, that is pO(data) = Pr(MO > ML| data) and the randomization probability for treatment L is pL(data) = 1 - pO(data). If at any point during the trial pL(data) > 0.90 (< 0.10) the trial will be terminated and treatment L will

be selected as superior (inferior). If the maximum number of patients is enrolled in the trial and pL(data) > 0.80 (< 0.20) treatment L will be selected as superior (inferior). If at any time during the trial we find that Pr(MO > 24 | data) < 0.05 or Pr(ML > 24 | data) < 0.05 we will suspend accrual to arm O or L, respectively, until this probability is 0.05 or greater.

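### The log-rank p-value and Cox 95% CI ignore the adaptive design and have no fixed data cut: with no effect, p<0.05 in about 8-9% of trials after 24-month follow-up and about 13-14% at stopping

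*Combined protocol and SAP*

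**What the plan says.** Section 6.1.1 (Primary Outcome) lists a Bayesian result first: "We will report the posterior probability that the letrozole arm has longer PFS than the observation arm". Kaplan-Meier curves follow, then "we will compare the PFS between the 2 arms with the log-rank test". A Cox model supplies the hazard ratio, for which "we will construct the 95% confidence interval for this hazard ratio". No significance level is given for the log-rank test. Nothing marks the test or the interval as adjusted or as nominal, and no analysis date is attached to either.

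The data come from an outcome-driven design:

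- Allocation (6.0): after the first 10 patients, "each successive patient is more likely to receive the treatment showing better results".
- Stopping (6.2): "If at any point during the trial pL(data) > 0.90 (< 0.10) the trial will be terminated".
- Suspension (6.2): if the posterior probability that an arm's median exceeds 24 months falls below 0.05, "we will suspend accrual to arm O or L, respectively, until this probability is 0.05 or greater".
- Follow-up (6.0): "We will follow all patients for at least 24 months following treatment". This sets a minimum follow-up. It does not say that the log-rank and Cox analyses wait for it after an early stop.

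**The concern.** The usual log-rank reference distribution and the usual Cox interval assume that the time of analysis and the allocation do not depend on the difference seen so far. Here both do. The trial ends when the observed difference is extreme, which is often partly chance. An arm that does badly by chance then receives fewer patients, so later data correct it less.

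Two consequences follow. If letrozole does nothing, small p-values appear too often and the 95% interval misses a hazard ratio of 1 too often. If letrozole works, an analysis run at stopping exaggerates the benefit. With no named cut, the size of the error also depends on when someone chooses to run the analysis.

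**Working it through.** **Inputs from the documents.** Section 6.0: "We will accrue a minimum of 10 patients and a maximum of 80 patients at a rate of 2 patients per month"; first 10 patients split 5 and 5; median PFS of 24 months on observation; at least 24 months of follow-up. Section 6.2: inverse gamma prior on each median with mean 24 and variance 57.6; allocation probability for letrozole equal to pL, the posterior probability that its median is the longer; stopping at 0.90/0.10; suspension at 0.05.

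**Assumptions.** Two-sided 0.05, to match the stated 95% interval; exponential PFS, no dropout and immediate event reporting; checks before each enrolment from patient 11, then monthly for 24 months after accrual; follow-up counted from the last enrolment. While one arm is suspended, patients go to the open arm; if both are, accrual waits.

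**Step 1: reproduce the plan's prior.** For shape a and scale b, the mean is b/(a-1) and the variance is mean²/(a-2). So a-2 = 24²/57.6 = 10, giving a = 12 and b = 24 × 11 = 264. The 2.5% and 97.5% points are 13.41 and 42.58 months, matching the 13.4 and 42.6 in section 6.2.

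**Step 2: posterior.** With d events and total exposure T in an arm, the median has posterior IG(12 + d, 264 + ln2 × T). With updated shapes aL, aO and scales bL, bO, pL is the Beta(aL, aO) distribution function at bL/(bL + bO), so no approximation is needed.

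**Step 3: no effect (medians 24 v 24; 20,000 trials, control 5,000).**

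| Design and cut | Log-rank p<0.05 | 95% CI coverage |
|---|---|---|
| Fixed 1:1, no stopping, no suspension | 5.0% | 95.3% |
| Planned design, 24 months after last enrolment | 8.2% | 92.2% |
| Planned design, at stopping | 13.7% | 89.7% |

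The Monte Carlo standard error at 8.2% is √(0.082 × 0.918/20,000) = 0.2 points. Repeat simulations with separate code gave 8.2-8.7% with follow-up and 12.4-15.3% at stopping, depending on the exact cut. Their fixed 1:1 controls gave 4.7-5.7%. About 22% of no-effect trials stop during accrual.

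**Step 4: sensitivity.** Twelve readings varied look frequency, post-accrual looks, accrual (1-4 per month), common median (18-36 months), Weibull shape (0.8-1.3) and suspension. With follow-up, rejection was 7-11% and coverage 90-93%. At stopping, they were 12-15% and 87.5-93%. No reading returned 5%.

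**Step 5: source of the excess (follow-up cut).** Allocation alone gives 7.1%, stopping alone 6.7% and suspension alone 6.1%. Within the full design suspension hardly matters: removing it moved a repeat run from 8.2% to 8.1%.

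**Step 6: when letrozole works (control median 24; 10,000 trials each).**

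| True HR | Coverage, at stopping / follow-up | Median estimated HR, at stopping / follow-up |
|---|---|---|
| 0.80 | 92.3% / 92.8% | 0.77 / 0.79 |
| 0.67 | 95.9% / 94.1% | 0.58 / 0.65 |
| 0.50 | 97.4% / 94.5% | 0.43 / 0.47 |

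**The case against.** The strongest reply is that nothing in the plan turns on this test. Stopping and selection use only the posterior, the log-rank test has no stated level or success rule, and this is a phase II trial of at most 80 patients. On that view a sentence calling the frequentist results nominal is enough, and simulated p-values with test inversion are out of proportion. It is true that no decision is affected and that the 5% is assumed. But the 95% on the interval is the plan's own figure, and at no effect the interval does not achieve it at either cut.

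Other points stand in part:

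- The follow-up sentence in 6.0 has no exception for an early stop. If it governs the analysis, 8-9% is the relevant figure and 13-14% does not arise. Section 6.1.1 does not say so.
- Arm suspension adds almost nothing in the full design. Allocation and stopping drive the excess, and each does so alone.
- Roughly half of the false rejections go against letrozole. False results in its favour are about 4.0-4.5% with follow-up, against 2.5%.
- At stopping, coverage exceeds 95% for large effects, so under-coverage is not universal.
- Table 1 is not in the supplied text. Whether it covers look timing or the data cut is unknown, and this is not counted against the plan.

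**Conclusion.** The concern holds, and the plan should be changed, although the Bayesian selection rule is untouched. With no effect, the log-rank test as written rejects in about 8-9% of trials after 24-month follow-up and about 13-14% at stopping; the 95% interval covers about 92% and 90%. The fixed 1:1 controls show that the design causes the excess, not the small sample. The shortfall in coverage is largest at no effect and shrinks as the true effect grows. An analysis at stopping overstates a real benefit: the median estimate is 0.58 when the true hazard ratio is 0.67.

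The sizes rest on the assumptions listed with the check, chiefly the two-sided 0.05 level and the look schedule. The direction held under every reading tried.

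**What to change.** 1. State one data cut for the log-rank and Cox analyses: 24 months after the last enrolment, including after an early stop.
2. Take the log-rank p-value from the null distribution obtained by simulating the actual allocation, suspension and stopping algorithm, with the common PFS distribution estimated from the pooled data. Allowing for stopping alone is not enough. Re-randomisation is an alternative if the trial reaches 80 patients; after an early stop, re-run sequences may need patients who were never enrolled.
3. For the hazard ratio, either invert that simulated test over a grid of hazard ratios, or report the Cox interval as nominal and unadjusted for the adaptive design, with its simulated coverage.
4. Keep the posterior as the primary result.

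A single widening factor would not work. With follow-up and a control median of 24 months, the multiplier that gives 95% coverage is 2.19 at HR 1, 2.14 at 0.80, 2.09 at 0.67 and 1.94 at 0.50.

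The remedy was checked at the follow-up cut with control medians of 18, 24 and 36 months (6,000 trials per cell). Rejection under no effect was 4.8-5.4%, and coverage of the inverted interval was 94.1-95.4% for hazard ratios of 1.0, 0.80, 0.67 and 0.50. This check and the multipliers were not repeated with separate code.

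The cost is SAP wording and computing time. Section 6.0 already reports simulations of the design, so the algorithm should exist in code. The labelling option for the interval needs one sentence and a coverage table. The p-value becomes less favourable: with follow-up, the chance of p<0.05 falls from about 30% to 22% at medians 24 v 36, and from about 59% to 51% at 24 v 48.

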6.1.2 Secondary Outcome

We will estimate the overall survival (OS) with the Kaplan-Meier product-limit estimator for each arm, and we will compare the OS between the 2 arms with the log-rank test. We will model OS with the Cox proportional hazards regression model to estimate the hazard ratio for treatment (letrozole : observation), and we will construct a 95% confidence interval for this hazard ratio.

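### The treatment-only log-rank and Cox analyses may be distorted if prognosis drifts during accrual, because adaptive allocation can tie treatment to enrolment date

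*Combined protocol and SAP*

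**What the plan says.** For PFS, section 6.1.1 states "we will compare the PFS between the 2 arms with the log-rank test" and begins the next sentence "We will model PFS with the Cox", with treatment as the only term named. Section 6.1.2 does the same for OS: "we will compare the OS between the 2 arms with the log-rank test", with a matching Cox model.

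Allocation is not constant. Section 6.0 plans: "We will accrue a minimum of 10 patients and a maximum of 80 patients at a rate of 2 patients per month". It continues: "The first 10 patients will be randomized fairly between the 2 treatment arms". After that "the randomization will become unbalanced in favor of the treatment" with the better average PFS, "so that each successive patient is more likely to receive the treatment showing better results". Section 6.2 sets the randomisation probability of an arm equal to the posterior probability that it has the longer median PFS. It stops the trial when that probability passes 0.90 or 0.10, and it can suspend accrual to one arm.

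No section names stratification by, or adjustment for, enrolment date or period, and none names a re-randomisation test. Section 5.0 requires a registration date for every registrant.

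**The concern.** Under this rule a patient's chance of receiving letrozole depends on when she enters. Within any one trial, the arm favoured late holds more late patients. If late patients do better or worse for reasons unrelated to treatment, such as referral, surgery or imaging, a model with treatment alone attributes part of that difference to treatment. With fixed 1:1 allocation the two arms share the drift almost equally and the problem hardly arises.

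At stake are the hazard ratio, its 95% interval and the log-rank p-value that the plan promises for PFS and OS. Readers are likely to cite these even though the selection rule is Bayesian.

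**Working it through.** **1. Inputs and a check on the plan's own figure.** Section 6.2 gives an inverse gamma prior with mean 24 and variance 57.6.
- Shape = 24²/57.6 + 2 = 12. Scale = 24 × (12 − 1) = 264.
- The middle 95% is then 13.41 to 42.58 months, which reproduces the stated 13.4 to 42.6.
- Accrual lasts at most 80/2 = 40 months. The run-in takes 10/2 = 5 months, so allocation adapts for at most 35 months.

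**2. Assumptions for the simulations.**
- PFS is exponential, with posterior inverse gamma (12 + events, 264 + ln 2 × exposure).
- One patient enters every half month, and the rules of 6.2 (stopping and arm suspension) are checked at each entry after patient 10.
- The analysis is 24 months after the last entry, at a two-sided 5% level. The documents set no such level.
- The documents give no drift. It is assumed log-linear, with the hazard multiplied by k over 40 months. As the median is ln 2/hazard, k = 0.5 doubles the median and k = 0.8 raises it by a quarter.

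**3. Is adaptive allocation the cause?** Both medians start at 24 months, with 4,000 trials per setting (Monte Carlo standard error about 0.5 points). Rejection rates:

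| k | Adaptive, unstratified | Adaptive, stratified by 10-month enrolment block |
|---|---|---|
| 1 | 8.5% | 7.5% |
| 0.67 | 10.4% | 8.3% |
| 0.5 | 11.4% | 7.7% |
| 0.33 | 12.5% | 7.9% |
| 1.5 | 6.6% | 8.1% |
| 2 | 5.8% | 8.8% |

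Fixed 1:1 allocation with the same stopping rule gives 6.5% to 7.3% whatever the drift. Without early stopping, fixed allocation gives 5.0% to 5.2%, while adaptive allocation gives 6.7% (k = 1), 11.6% (k = 0.5), 14.9% (k = 0.33) and 2.9% (k = 2). So the sensitivity to drift comes from adaptive allocation. The excess over 5% without drift comes from early stopping and adaptive allocation.

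**4. Does a linear enrolment-date term help?** Null Cox rejection, 3,000 trials per setting:

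| k | Treatment only | Treatment + enrolment date |
|---|---|---|
| 1 | 7.7% | 7.8% |
| 0.8 | 8.8% | 8.3% |
| 0.67 | 9.7% | 8.2% |
| 0.5 | 11.8% | 8.3% |
| 2 | 4.8% | 7.5% |

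A separate run of 2,500 trials per setting gave 7.8% v 7.7% (k = 1), 9.7% v 7.7% (k = 0.67), 12.4% v 9.0% (k = 0.5) and 5.6% v 9.0% (k = 2). At k = 0.5 the 95% interval covered the truth in 87.6% of trials unadjusted and 91.0% adjusted.

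**5. Effect on the estimate.** With medians 24 v 36, the true hazard ratio is 24/36 = 0.667. Across drifts the unadjusted median estimate ran from 0.605 to 0.686, and the adjusted one from 0.633 to 0.641. On the log scale the spreads are ln(0.686/0.605) = 0.126 and ln(0.641/0.633) = 0.013. The standard deviation of the unstratified log hazard ratio without drift was 0.393, so the unadjusted spread is about 0.126/0.393 = 0.32 of one standard deviation.

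**6. Cost without drift.** At hazard ratio 0.667, power was 29.0% unadjusted v 27.7% adjusted in one run, and the loss was under 1 point in another. At hazard ratio 0.50 it was 59.3% v 57.3%. Stratifying by 10-month block costs more at 0.667: 29.6% v 26.2%.

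**The case against.** Five arguments weigh against the point.

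- **No evidence of drift.** A reader might infer that the planned hazard ratio, interval and p-value are wrong as they stand. The documents do not support that. They describe one centre (3.3.1), one set of eligibility criteria (3.3.2) and scheduled imaging (3.5.2). With k = 0.8 the gain is only 8.8% to 8.3%, and 40 months is a maximum that early stopping shortens. This stands, and the point is conditional for that reason.
- **Not the decision rule.** Allocation, stopping and selection use the posterior probability in 6.2, which also has no time term and which this fix leaves alone. This stands. It limits what the fix achieves, but it does not protect the reported hazard ratio.
- **Adjustment can move rejection away from 5%.** With k = 2 it goes from 4.8% to 7.5%. This is true, but the lower figure arises because drift offsets the excess from stopping and adaptation. In the 2,500-trial run with k = 2 and true hazard ratio 0.667, power was 20.6% unadjusted v 26.4% adjusted. The unadjusted estimate can then also lie nearer the truth (0.679 v 0.639), again because two biases offset.
- **The adjusted p-value is still not nominal.** A reader might infer that adjustment restores 5%. It does not.
- **Limited testing.** The linear term was tried only against monotone drift, and only for PFS. This stands.

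Table 1, cited in 6.0, is not in the text available, so whether its six scenarios include drift cannot be said. That would not change the models in 6.1.

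**Conclusion.** The point holds in conditional form. Treatment can be correlated with enrolment date by design, and the planned analyses name no term for it. If prognosis improves during accrual, the false-positive rate rises (about 8% to about 12% if the hazard halves over 40 months) and a true effect is exaggerated. If prognosis worsens, rejection falls and the hazard ratio is pulled towards 1. The size is modest: across the drifts tried, the estimate moves by about a third of one standard deviation.

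The figures rest on exponential PFS, log-linear drift of assumed size, continuous monitoring and an assumed 5% level. The case for acting is prespecification: drift cannot be known in advance, and choosing the adjustment after seeing the data would be open to criticism.

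**What to change.** In 6.1.1 and 6.1.2, prespecify a Cox model with treatment plus enrolment date (registration date, as a linear term in months since the first patient). Take the reported hazard ratio and 95% interval from it, and show the unadjusted Cox and log-rank results beside it.

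State in the plan that:
- the adjustment removes only the drift component;
- about 8% rejection remains at a nominal 5%, owing to early stopping and adaptive allocation, so the p-value should not be presented as exact;
- the posterior probability used for allocation, stopping and selection in 6.2 is still not adjusted for enrolment time.

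No new data are needed. The cost is about 1 to 2 points of power at most if there is no drift. For OS the change follows by the same reasoning, but its effect there was not simulated.

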6.1.2 Secondary Outcome

We will estimate the overall survival (OS) with the Kaplan-Meier product-limit estimator for each arm, and we will compare the OS between the 2 arms with the log-rank test. We will model OS with the Cox proportional hazards regression model to estimate the hazard ratio for treatment (letrozole : observation), and we will construct a 95% confidence interval for this hazard ratio.

6.2 Technical Details

Let MO and ML be the median PFS for treatments "observation" (O) and "letrozole" (L), respectively. We assume that MO and ML each have an inverse gamma prior distribution with mean 24 months and variance 57.6 months. The middle 95% of this prior distribution is between 13.4 and 42.6 months.

For each patient, the randomization probability for treatment O will be the posterior probability that it has the longer PFS, that is pO(data) = Pr(MO > ML| data) and the randomization probability for treatment L is pL(data) = 1 - pO(data). If at any point during the trial pL(data) > 0.90 (< 0.10) the trial will be terminated and treatment L will

be selected as superior (inferior). If the maximum number of patients is enrolled in the trial and pL(data) > 0.80 (< 0.20) treatment L will be selected as superior (inferior). If at any time during the trial we find that Pr(MO > 24 | data) < 0.05 or Pr(ML > 24 | data) < 0.05 we will suspend accrual to arm O or L, respectively, until this probability is 0.05 or greater.

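### Does the suspension rule in section 6.2 need a stated end when both arms are suspended, and a stated allocation when only one is?

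*Combined protocol and SAP*

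**What the plan says.** Section 6.0 sets the size of the trial ("We will accrue a minimum of 10 patients and a maximum of 80 patients") and its benchmark: "Patients treated with standard of care (observation) have median progression-free survival (PFS) of 24 months". Section 6.2 gives four rules.

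- Allocation: "For each patient, the randomization probability for treatment O will be the posterior probability that it has the longer PFS"; letrozole gets the complement, pL.
- Early stop: "If at any point during the trial pL(data) > 0.90 (< 0.10) the trial will be terminated".
- Final selection at 0.80/0.20, which opens with the condition "If the maximum number of patients is enrolled in the trial". Section 6.0 agrees: "if all 80 patients are enrolled, then a treatment will be selected".
- Suspension, triggered for each arm separately by "Pr(MO > 24 | data) < 0.05 or Pr(ML > 24 | data) < 0.05", after which "we will suspend accrual to arm O or L, respectively, until this probability is 0.05 or greater".

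Section 6.0 does not mention suspension. The reporting in section 6.1.1 (posterior probability, Kaplan-Meier, log-rank, Cox) does not depend on how many patients were enrolled.

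**The concern.** The rules leave two situations open.

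1. **Both arms suspended.** Each arm is judged on its own against 24 months, so both can be closed at once. Below 80 patients the 0.80/0.20 rule cannot apply. If pL lies between 0.10 and 0.90, enrolment resumes only if further follow-up lifts one probability back to 0.05. Once every enrolled patient has progressed, the posterior no longer moves and the halt is permanent. The choice to wait, override or close would then be made with pL already known.

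2. **One arm suspended.** The randomisation probability is defined for every patient, but it cannot be applied while an arm is closed, and no replacement is given. If all new patients go to the open arm, they have no concurrent comparator. They may also be sent there on the historical benchmark while pL is far from decisive.

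At stake would be an enrolment with no prespecified end and some loss of randomised comparison.

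**Working it through.** **Prior (section 6.2).** Mean 24 and variance 57.6 give shape 2 + 24²/57.6 = 12 and scale 24 × (12 − 1) = 264. The 2.5% and 97.5% points of this inverse gamma are 13.41 and 42.58 months, which reproduces the stated 13.4 to 42.6.

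**When the trigger fires.** Assume exponential PFS, since the text names no likelihood. With d events and T patient-months in an arm, the posterior is inverse gamma(12 + d, 264 + ln2 × T). Then Pr(M > 24) is the probability that a Gamma(12 + d, 1) variable lies below (264 + ln2 × T)/24. For d = 10 the 5% point is 14.89, so the limit is T = (24 × 14.89 − 264)/0.693 = about 135. The observed median is then 0.693 × 135/10 = about 9.3 months. For 20 events the limits are about 426 patient-months and 14.8 months; for 40 events, about 1,030 and 17.8. An arm must do far worse than 24 months before it closes.

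**Double suspension.** Settings: 2 patients per month, first 10 split 5:5, then allocation by pL, checks at each arrival from patient 10, patients sent to the open arm when one is closed, 10,000 trials per scenario, events detected at once. Stalled means 36 months of cumulative waiting, an assumed limit.

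| True medians, both arms | Observation suspended | Both suspended | Stalled |
|---|---|---|---|
| 24 | 3% | 0.2% | under 0.1% |
| 20 | 14% | 3% | 0.7% |
| 18 | 27% | 10% | 4% |
| 17 | 37% | 17% | 8% |
| 15 | 62% | 41% | 28% |

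Double suspensions that reopened did so after a median of 1 to 1.5 months. Section 3.5.2 schedules CT every 24 weeks. If events are recorded at those visits, the three rates become 5-16%, 0.4-3% and 0.1-0.8% at 17 months, and 15-33%, 2-12% and 0.8-5% at 15 months. The low end counts exposure to the calendar date, the high end to the last visit. With detection at the 12-weekly examinations, the rates at 17 months are 17-26%, 4-9% and 1-3%. If the 17 or 15 months is already a visit-recorded median, the reduction does not fully apply.

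**One-arm suspension.** A separate run of 2,000 trials per scenario finds one arm suspended alone at some point in 5.6% of trials at 24/24 (observation/letrozole), 20% at 18/24, 18% at 12/36 and 51% at 12/24. This gap therefore needs only one short arm. The quantity that matters is how many assignments differ from what pL would have given:

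| Medians O/L | Assignments changed | Patients per trial |
|---|---|---|
| 24/24 | 0.14% | 0.1 |
| 18/24 | 0.65% | 0.5 |
| 12/24 | 2.1% | 1.3 |
| 17/17 | 2.7% | 2 |

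Rough check at 17/17: 10% of patients enter during a one-arm suspension, and the median pL when observation is first suspended is 0.67, so about 10% × (1 − 0.67) = 3.3% would be redirected, close to 2.7%. The same product at 15/15 is 17% × (1 − 0.62) = 6.5%, probably somewhat high for the same reason.

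**Other readings.** If patients randomised to the closed arm are simply not entered, the three rates at 17/17 move from 37%, 17% and 8% to 39%, 20% and 10%. Pausing all accrual matters more: at 12/24 the mean enrolment is 54.8 instead of 60.5, and 12.9% of trials instead of 27.7% reach 80. But the text suspends accrual to the affected arm, not to the trial, so a full pause is not its natural reading.

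**What completing the rule would do.** Two versions were simulated: (a) end enrolment on a double suspension, at once or after 3 months, and apply 0.80/0.20 at 24 months' follow-up; (b) keep randomising by pL while both arms are below the benchmark. At equal medians every selection is false.

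| Scenario O/L | As written | (a) | (b) |
|---|---|---|---|
| 15/15, any selection | 12 + 12 = 24% | 13 + 13 = 26% | 14 + 14 = 28% |
| 12/12, any selection | 5 + 5 = 10% | 7 + 7 = 14% | 10 + 10 = 20% |
| 15/22.5, letrozole selected | 73% | 72-73% | 73% |
| 17/25.5, letrozole selected | 74% | 73-74% | 74% |
| 22.5/15, observation selected | 71% | 70% | 70-71% |

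False selection rises because trials that would have stalled now reach a decision; correct selection does not improve.

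**The case for a change.** The best argument for a change is that suspension exists for the case of poor PFS, and that is where it is incomplete. The plan's own prior puts 13.4 months inside its middle 95%. Averaged over that prior with events seen at once, both arms are suspended in 3.5% of trials and stalled in 1.6% if the medians are independent, or 8% and 5% if they share one value. A rule written beforehand would avoid a choice made with pL in view. Section 7.1.1 offers an amendment route, but a generic one.

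Much of this stands as description: the text is silent on both points, and a lasting double suspension would need a decision. It does not carry through to a change in design. The two ways of completing the rule are competing preferences: (a) uses 0.80/0.20 below the enrolment for which sections 6.0 and 6.2 reserve it, and (b) switches the suspension off when both arms fall below the benchmark. Neither restores a concurrent comparator: 8-9% of patients at 17/17 would still enter during a one-arm suspension, against 10% as written.

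The worry about steering patients to letrozole is also weaker than it looks. The rule is symmetric between the arms, and at pL of 0.6 to 0.7 the ordinary allocation already sends 60-70% of patients there.

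**Conclusion.** The omissions are real, but no change to the plan follows. At the planned 24 months, which section 2.0 also supports by putting recurrence at about half of patients within two years, double suspension occurs in about 0.2% of trials and stalling in under 0.1%. It becomes common only if both medians are well below 24 months, and much less so under the imaging schedule. The allocation gap can arise with one short arm, but filling it in the natural way, by entering patients on the open arm, moves about 0.7% to 3% of assignments at 18/24, 12/24 and 17/17. A trial held below 80 can still be reported under section 6.1.1; what it lacks is a rule that closes enrolment, and a lasting halt can be handled by amendment. The completed rules gain no correct selections and cost some false ones.

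This rests on exponential PFS, accrual of 2 per month, the assumed 36-month limit for stalling and the redirect reading. Table 1 is not in the text available, so whether its simulations included the suspension rule cannot be judged. A query to the study statistician on the allocation used, the handling of a lasting double suspension and the content of Table 1 is enough.
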